8.2.21. Hospital Anxiety and Depression Scale (HADS)

The HADS-anxiety and HADS-depression scores will be summarized at each post-baseline visit (Week 4, Week 12, and Week 24).

In addition, at each post-baseline visit until Week 12, the change from baseline will be modelled using the same MMRM model used for the analysis of the primary endpoint. LS mean difference between the dupilumab and placebo group, the corresponding 95% CI of the difference and two-sided p-values will be provided. All p-values except for Week 12 will be considered nominal.

8.2.22. Relationship between variables relating to sleep disturbances and objective and subjective parameters associated with AD.

Relationship between variables (change from baseline and percent change from baseline) relating to sleep disturbances and objective and subjective parameters associated with AD will be explored. Pearson correlation coefficient and p-value will be provided by visit. For the PSG subset, Spearman correlation coefficient and p-value will be provided by visit.

Variables relating to sleep disturbances include:

- Sleep quality NRS
- SE, TST, WASO, and SOL based on actigraphy data
- SE, TST, WASO, and SOL based on sleep diary data
- SCORAD sleep VAS
- PROMIS Sleep Related Impairment SF8a total score
- SE, TST, WASO, and SOL based on the PSG data
- PVT variables: total errors, number of lapses, mean reciprocal response time, mean fastest response time, and mean slowest reciprocal response time
- ANAM variables: mean response time, percentage of correct response and throughput for running memory, mathematical processing and procedural reaction time.

Variables relating to objective and subjective parameters associated with AD include:

- SCORAD total score
- EASI total score
- POEM total score
- DLQI total score
- Peak pruritus NRS

The correlations at baseline, Week 12 and change from baseline to Week 12 will be analyzed by group as defined below:

- Group 1: Sleep quality NRS versus EASI total score, SCORAD total score, POEM total score, DLQI total score, and Peak Pruritus NRS

- Group 2: Sleep diary versus Actigraphy (corresponding measure, SE, TST, WASO, and SOL), POEM total score, SCORAD total score, PROMIS Sleep Related Impairment SF8a total score.
- Group 3: PSG versus Actigraphy (corresponding measure), sleep diary (corresponding measure) on the subset of PSG patients.
- Group 4: Sleep quality NRS versus PVT variables, ANAM variables, WPAI-AD variables and days missed from school or from work.
- Group 5: Sleep quality NRS versus PVT variables, ANAM variables, WPAI-AD variables and days missed from school or from work for Week 24, and Change from baseline to Week 24

For actigraphy and sleep diary data, the weekly averages will be used for correlations. Additionally, for Group 3, the same day assessment (not the average) will be used.

Additionally, relationship between PSG and actigraphy data for the PSG analysis set will be analyzed by providing scatter plots for each of the PSG parameters versus the corresponding actigraphy parameters. For actigraphy data, the same day assessment (not the average) as those of the PSG data will be used.

8.2.23. Multiplicity issues

The overall type-I error rate will be controlled at the two-sided 0.05 level using a sequential testing procedure. In order for any secondary endpoints to be eligible for being declared significant, the primary endpoint must be significant at 0.05 significance level. The secondary endpoints will be tested following the hierarchical testing procedure with a pre-specified order, that is, inferential conclusions about successive secondary endpoints require statistical significance at 0.05 significance level of the previous one.

The following key secondary endpoints will be included in the multiplicity adjustment scheme and tested in the following order:

1. Percent change from baseline to Week 12 in peak pruritus NRS
2. Change from baseline to Week 12 in SCORAD total score
3. Change from baseline to Week 12 in SCORAD sleep VAS
4. Change from baseline to Week 12 in PROMIS Sleep Impairment SF8a score
5. Change from baseline to Week 12 in TST based on actigraphy data
6. Change from baseline to Week 12 in SE based on actigraphy data
7. Change from baseline to Week 12 in WASO based on actigraphy data
8. Change from baseline to Week 12 in SOL based on actigraphy data

Each endpoint will be tested at 0.05 (two-sided) level of significance. If at any step the null statistical hypothesis of no treatment difference is not rejected, the endpoints listed after that step will be reported at nominal level, otherwise will be technically eligible for being declared significant. Regardless of eligibility for being declared significant, all endpoints (non-key secondary and exploratory) will be tested at 0.05 (two-sided) level of significance and reported at nominal level.

9. Safety Analysis

All safety results will be summarized separately within the double-blind treatment period and the overall period (combined double-blind and OLE periods), using the Safety analysis set by actual treatment group and overall.

The observation periods include:

- The **pre-treatment** period is defined as the time from the signed informed consent date up to first administration of the IMP.
- The **randomized on-treatment** period is defined as the time from the first administration of the IMP (on Day 1) to the last administration of the IMP prior to Week 12 + 14 days if the patient does

not enter the OLE period, or until prior to the loading dose at Week 12 if the patient enters the OLE period.

- The **open-label extension on-treatment** period is defined as the time from the loading dose at Week 12 to the last administration of the IMP + 14 days.
- The **treatment-emergent adverse event (TEAE)** period is defined as the time from the first administration of the IMP (on Day 1) to the last administration of the IMP + 14 days (both randomized on-treatment and open-label extension on-treatment periods).

9.1. Adverse Events

The adverse event observation periods include:

- **Pre-treatment adverse events** are adverse events that developed or worsened or became serious from the signed informed consent date up to the first administration of the IMP.
- **Treatment-emergent adverse events** are adverse events that developed or worsened or became serious during the TEAE period.
- **Post-treatment adverse events** are adverse events that developed or worsened or became serious after TEAE period.

The primary focus of adverse event reporting will be on treatment-emergent adverse events. Pre-treatment and post-treatment adverse events will be summarized separately.

All adverse events will be coded to a LLT, PT, HLT, HLGT, and associated primary SOC using the version of Medical Dictionary for Regulatory Activities (MedDRA) currently in effect at Sanofi at the time of each database lock.

Adverse events will be recorded from the time of signed informed consent until the end of the study or the resolution/stabilization of all SAE and AESI.

If an adverse event date/time of onset (occurrence, worsening, or becoming serious) is incomplete, an imputation algorithm will be used to classify the adverse event as pre-treatment, treatment-emergent, or post-treatment. The algorithm for imputing date/time of onset will be conservative and will classify an adverse event as treatment-emergent unless there is definitive information to determine it is pre-treatment or post-treatment. Details on classification of adverse events with missing or partial onset dates are provided in [Section 15.4.4](#).

Adverse event will be summarized by primary SOC, HLGT, HLT, and PT, sorted in alphabetical order for each treatment group using number and percentage of patients experiencing an adverse event. Multiple occurrences of the same event in the same patient will be counted only once in the tables within a treatment phase. The denominator for computation of percentages is the safety analysis set within each treatment group.

Sorting within tables ensures the same presentation for the set of all adverse events within the observation period (pre-treatment, treatment-emergent, and post-treatment). For that purpose, the table of all treatment-emergent adverse events presented by primary SOC and PT (sorted by the internationally agreed SOC order and decreasing frequency of PTs within SOC in the dupilumab group) will define the presentation order for all other summaries unless otherwise specified. In case of equal frequency regarding PTs, alphabetical order will be used.

On top of the analysis planned below, all TEAEs, all treatment-emergent SAEs, TEAEs leading to permanent treatment discontinuation and TEAEs leading to deaths will be summarized by treatment group and by trial impact (disruption) due to COVID-19.

Overview summaries of the number and percentages of patients within the following categories will be provided by treatment group and overall, for pre-treatment AEs, TEAEs during double-blind treatment period, TEAEs during the study, and post-treatment AEs.

- Any TEAE
- Any study drug related TEAE
- Any Severe TEAE
- Any Serious TEAE
- Any TEAE leading to permanent treatment discontinuation
- Any TEAE of special interest
- Any Serious TEAE of special interest
- Any TEAE leading to death

The overview summaries for TEAEs during the double-blind treatment period and during the overall period will be provided on the safety analysis set and the analysis set with trial impact (disruption) due to COVID-19.

Individual listings (AEs, SAEs, AEs leading to permanent treatment discontinuation, AEs leading to death, AESI and all AEs in treated patients but not considered as randomized) will be provided to support the summary tables based on the safety analysis set.

9.1.1. Incidence of Adverse Events

The following TEAE summaries will be generated for the safety analysis set, for each treatment group and overall.

- All TEAEs presented by primary SOC and PT, showing the number and percentage of patients with at least 1 TEAE, sorted by internationally agreed order of primary SOC and by decreasing incidence of PTs within each SOC in the dupilumab group. This sorting will be applied to all other summaries, unless otherwise specified.
- All TEAEs presented by primary SOC, HLGT, HLT, and PT, showing the number and percentage of patients with at least 1 TEAE, sorted by internationally agreed order of primary SOC. The other levels (HLGT, HLT, PT) will be presented in alphabetical order
- All pre-treatment AE presented by primary SOC and PT, showing number and percentage of patients with at least 1 TEAE, sorted by internationally agreed order of primary SOC and by decreasing incidence of PTs within each SOC in the dupilumab group.
- All treatment-emergent COVID-19 related adverse events presented by primary SOC and PT, showing number and percentage of patients with at least 1 treatment-emergent COVID-19 related AE, sorted by internationally agreed order of primary SOC and by decreasing incidence of PTs within each SOC in the dupilumab group.
- All post-treatment AE presented by primary SOC and PT, showing number and percentage of patients with at least 1 TEAE, sorted by internationally agreed order of primary SOC and by decreasing incidence of PTs within each SOC in the dupilumab group.
- Common TEAEs (PTs with an incidence $\geq 5\%$ in any treatment group) by primary SOC, HLGT, HLT, and PT, sorted by internationally agreed order of SOC. The other levels (HLGT, HLT, PT) will be presented in alphabetic order.

Search criteria for COVID-19 related AE will be provided by SANOFI.

9.1.2. Relationship of Adverse Events to Study Drug

The following TEAE summaries will be generated for the safety analysis set, for each treatment group and overall.

- All TEAEs by relationship, presented by primary SOC, HLGT, HLT and PT, showing the number and percentage of patients with at least 1 TEAE, sorted by internationally agreed order of primary SOC. The other levels (HLGT, HLT and PT) will be presented in alphabetical order

9.1.3. Severity of Adverse Event

The following TEAE summaries will be generated for the safety analysis set, for each treatment group and overall.

- All TEAEs by maximal severity, presented by primary SOC and PT, showing the number and percentage of patients with at least 1 TEAE by severity (i.e., mild, moderate, severe).

9.1.4. Serious Adverse Events

The following TEAE summaries will be generated for the safety analysis set, for each treatment group and overall.

- All serious TEAEs presented by primary SOC, HLGT, HLT and PT, showing the number and percentage of patients with at least 1 serious TEAE, sorted by internationally agreed order of primary SOC. The other levels (HLGT, HLT and PT) will be presented in alphabetical order.
- All serious TEAEs by relationship, presented by primary SOC, HLGT, HLT and PT, showing the number and percentage of patients with at least 1 TEAE, sorted by internationally agreed order of primary SOC. The other levels (HLGT, HLT and PT) will be presented in alphabetical order

9.1.5. Adverse Events Leading to Permanent Treatment Discontinuation

The following TEAE summaries will be generated for the safety analysis set, for each treatment group and overall.

- All TEAEs leading to permanent treatment discontinuation, presented by primary SOC, HLGT, HLT and PT, showing the number and percentage of patients with at least 1 serious TEAE, sorted by internationally agreed order of primary SOC. The other levels (HLGT, HLT and PT) will be presented in alphabetical order

9.1.6. Adverse Events Leading to Study Discontinuation

Not applicable

9.1.7. Adverse Events of Special Interest (AESI)

As defined in [Appendix 15.6](#), Adverse Events of Special Interest (AESI) include:

- Anaphylaxis
- Systemic or severe hypersensitivity reactions
- Malignancy (except in situ carcinoma of the cervix, non-metastatic squamous or basal cell carcinoma of the skin)
- Helminthic infections
- Suicide-related events
- Any type of conjunctivitis or blepharitis (severe or serious)
- Keratitis
- Pregnancy occurring in a female patient or in a female partner of male patient administered IMP/NIMP
- Symptomatic overdose of IMP/NIMP

The following TEAE summaries will be generated for the safety analysis set, for each treatment group and overall.

- All TEAEs of Special Interest, presented by primary SOC, HLGT, HLT and PT, showing the number and percentage of patients with at least 1 serious TEAE, sorted by internationally agreed order of primary SOC. The other levels (HLGT, HLT and PT) will be presented in alphabetical order
- All serious TEAEs of Special Interest, presented by primary SOC, HLGT, HLT and PT, showing the number and percentage of patients with at least 1 serious TEAE, sorted by internationally agreed order of primary SOC. The other levels (HLGT, HLT and PT) will be presented in alphabetical order

9.1.8. Adverse Events Leading to Death

The following TEAE summaries will be generated for the safety analysis set, for each treatment group and overall.

- All TEAEs leading to death (death as an outcome on the eCRF form “Adverse Event” as reported by Investigator), presented by primary SOC, HLGT, HLT and PT, showing the number and percentage of patients with at least 1 serious TEAE, sorted by internationally agreed order of primary SOC. The other levels (HLGT, HLT and PT) will be presented in alphabetical order

9.1.9. Death

The following summaries of deaths will be generated for the safety analysis set, for each treatment group and overall.

- Number and percentage of patients who died during the overall period and cause of death by study period.
- Number and percentage of non-randomized patients or randomized but not treated patients who died.

A listing of all patients who died during the study will be provided.

9.2. Clinical Laboratory Evaluations

Urine human chorionic gonadotropin pregnancy test (as needed for women of childbearing potential) will be performed by the local laboratory, at designated visits. No other laboratory tests are planned in protocol.

Additional tests may be performed at any time during the study as determined necessary by the Investigator or required by local regulations; any clinically significant abnormal lab values will be included in the adverse event analyses.

No laboratory variables will be summarized for this study.

9.3. Vital Sign Measurements

Vital signs including height, weight, heart rate (HR), sitting systolic (SBP) and diastolic blood pressure (DBP), temperature and respiration rate, will be collected at screening visit and all subsequent visits before injection and at 30 minutes (\pm 10 minutes) post-injection.

The vital sign results will be summarized for the safety analysis set by treatment group using descriptive statistics and for each visit or study assessment (baseline, each-post-baseline time point, last on-treatment value).

The Potentially Clinically Significant Abnormalities (PCSA) at any time during the TEAE period will be summarized for the safety analysis set by treatment group and overall, using number and percentage. The PCSAs are provided in [Section 15.7](#).

All measurements collected during the TEAE period, including values from unscheduled visits, will be considered for the PCSA summaries. The summaries will include patients in the safety analysis set who have at least 1 assessment performed during the TEAE period. When a PCSA definition involves a change from baseline value, patients must also have a baseline value to be included in the summaries.

A listing of patients with at least 1 post-baseline PCSA will be provided and will display the patient's profile over time of all vital sign parameters.

Individual data listings will include the following flags:

- Baseline values will be flagged "B",
- Parameter values reaching a PCSA limit will be flagged (+, or - depending of the direction).

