3.3. Treatments

The dose selected in this study is the dose approved for the treatment of moderate to severe AD for Dupixent in US, EU, and all other countries that this study will be conducted.

Patients will receive either;

- Dupilumab 600 mg (2 x 300 mg dupilumab injections) on Day 1 (ie, the loading dose), followed by 1 dupilumab injection of 300 mg every two weeks (Q2W) until week 10, then 1 dupilumab + 1 placebo injection at Week 12 (to protect the blind while patients in placebo arm receive their loading dose), followed by 1 300 mg dupilumab injection Q2W with last injection at week 22 or
- Matching placebo for dupilumab (2 x 2mL placebo injections) on Day 1 (ie, the loading dose), then 1 placebo injection Q2W until week 10, and then 2 x 300 mg dupilumab injections at week 12 (ie, the loading dose), followed by dupilumab injections Q2W with last injection at week 22.

Non-investigational medical products

Starting on Day -7, all patients are required to undergo background treatment with medium-potency topical corticosteroids (TCS) [i.e., non-investigational medical products (NIMP)].

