For endpoints where measurements were only scheduled once for post-baseline (e.g., weight at week 24 and PSG at week 12), the measurement that is closest to the target day will be used.

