15.7. Potentially Clinically Significant Abnormalities (PCSA) Criteria

Table 15.7.1 Potentially Clinically Significant Abnormalities Criteria

CRITERIA for POTENTIALLY CLINICALLY SIGNIFICANT ABNORMALITIES for phase 2/3 studies (oncology excepted) (From BTD-009536 May 21, 2014)		
Parameter	PCSA	Comments
HR	≤ 50 bpm and decrease from baseline ≥ 20 bpm ≥ 120 bpm and increase from baseline ≥ 20 bpm	To be applied for all positions (including missing) except STANDING.
SBP	≤ 95 mmHg and decrease from baseline ≥ 20 mmHg ≥ 160 mmHg and increase from baseline ≥ 20 mmHg	To be applied for all positions (including missing) except STANDING.
DBP	≤ 45 mmHg and decrease from baseline ≥ 10 mmHg ≥ 110 mmHg and increase from baseline ≥ 10 mmHg	To be applied for all positions (including missing) except STANDING.
Weight	$\geq 5\%$ increase from baseline $\geq 5\%$ decrease from baseline	FDA Feb 2007

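### The only scheduled post-baseline weight falls on the last day of the period in which weight abnormalities are counted, so in-window V9 weights can be left out of that table

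*SAP*

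**What the plan says.** - **What is counted.** SAP Table 15.7.1, "Potentially Clinically Significant Abnormalities Criteria", flags a weight change from baseline of at least 5% in either direction.
- **When it is counted.** SAP 9.3: "The Potentially Clinically Significant Abnormalities (PCSA) at any time during the TEAE period will be summarized for the safety analysis set". It adds: "All measurements collected during the TEAE period, including values from unscheduled visits, will be considered for the PCSA summaries". A patient needs at least one assessment in that period, and a baseline value, to enter the summary.
- **When the period ends.** SAP section 9 runs the TEAE period from the first dose to "the last administration of the IMP + 14 days (both randomized on-treatment and open-label extension on-treatment periods". It does not say whether day 14 itself belongs to the period. SAP 7.1.2, defining concomitant medications with the same 14 days, excludes the boundary.
- **Last dose.** SAP 3.3, for the placebo arm: "followed by dupilumab injections Q2W with last injection at week 22". The dupilumab arm also ends at Week 22.
- **When weight is taken.** In the schedule (protocol 1.3, SAP 15.2) weight has its own row, marked at Screening 1 and V9 only. V9 is Day 169 ± 3, or earlier on premature discontinuation. SAP 15.5 names "weight at week 24 and PSG at week 12" as examples of measurements scheduled once after baseline. SAP 9.3, in contrast, lists weight and height among the signs collected at screening and every later visit.
- **Split by period.** SAP section 9: "All safety results will be summarized separately within the double-blind treatment period and the overall period".

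**The concern.** The cut-off and the measurement share a target day. Heart rate and blood pressure are measured at every visit, so a patient whose V9 comes a day late still has earlier values in the period. For weight there is no other scheduled value. A patient can follow the protocol, attend V9 inside its window and be weighed, yet contribute nothing to the weight abnormality count and, if the inclusion rule is applied per parameter, leave its denominator too.

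The denominator of a prespecified safety count would then depend on visit punctuality and on a boundary rule that the SAP does not state. If the split by period is also applied to weight, the double-blind version would hold almost no patients.

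**Working it through.** **Inputs**
- Last planned dose: Week 22 (SAP 3.3; protocol 6.1). No dosing window is stated.
- Weight: V9, Day 169 ± 3, so Days 166 to 172 (schedule).
- Cut-off: last dose + 14 days (SAP section 9).

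**Step 1: the day count.** With baseline as Day 1, day = 7 × week + 1.
- Week 24: 7 × 24 + 1 = 169, which reproduces the schedule's figure.
- Week 22: 7 × 22 + 1 = 155.
- Cut-off: 155 + 14 = 169, the V9 target day.

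**Step 2: who falls outside.** With the last dose on Day 155, a V9 on Days 170 to 172 is in window but after the cut-off. A V9 on Day 169 is in or out according to the boundary rule.

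**Step 3: the share.** Let gap = V9 day − last dose day. The excluded share is P(gap > 14) if day 14 counts and P(gap ≥ 14) if it does not. The documents give no distribution of visit or dose days, so each row is an assumption.

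| Assumed days | Day 14 included | Day 14 excluded |
|---|---|---|
| Dose Day 155; V9 even over Days 166–172 | 3/7 = 43% | 4/7 = 57% |
| Dose even over Days 152–158, independent of V9; V9 even | 21/49 = 43% | 28/49 = 57% |
| Dose Day 155; 50% of V9 on Day 169, rest even over the other six days | 3 × 0.50/6 = 25% | 50% + 25% = 75% |
| Dose Day 155; 90% of V9 on Day 169, rest even | 3 × 0.10/6 = 5% | 90% + 5% = 95% |
| Dose Day 152; V9 even over Days 166–172 | 6/7 = 86% | 7/7 = 100% |
| Dose Day 158; V9 even over Days 166–172 | 0/7 = 0% | 1/7 = 14% |

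SAP Table 15.5.1 gives the Week 24 target as study day 168, not 169. Centring an even ±3 day window there, with the dose on Day 155, gives 2/7 = 29% and 3/7 = 43%.

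**Step 4: the other outputs.** Table 15.5.1 gives weight an open-ended window, so a late V9 weight still counts as Week 24 in the by-visit summary. In SAP 9.3 the listing of patients with a post-baseline abnormality is not limited to the TEAE period. One value can therefore appear in both outputs and be missing from the abnormality count.

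**Step 5: the double-blind period.** No weight is scheduled between screening and V9. A double-blind weight table would draw only on patients whose V9 was brought forward by early discontinuation.

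**The case against.** **A 14-day cut-off is a legitimate on-treatment rule.** It is, and nothing here argues against it in general. The difficulty is pairing it with a single measurement placed on its last day.

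**SAP 9.3 says weight is taken at every visit, so in-period values would exist.** This does not hold. The schedule in both documents, Table 15.5.1 and the text of SAP 15.5 all give one post-baseline weight, and protocol 8.2.1 does not list weight among the vital signs. The same SAP sentence includes height, which the schedule marks at screening only.

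**The size is unknown.** This stands. A reader might infer that about half of completers' weights are excluded. That follows only if visits spread evenly over seven days. Visits may cluster on the target day, and the Week 22 home dose is tied to the Week 20 visit (protocol 6.3), so dose and V9 may shift together. Nor can a number of patients be given: the 150 evaluable participants in the protocol refer to Week 12, and no Week 24 completer count is stated.

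**Nothing is discarded.** This also stands. A reader might infer that the weights are lost to the analysis. They leave the abnormality summary only; the by-visit summary and the listings keep them.

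**Little depends on it.** Largely right. Weight is not an endpoint. By Week 24 all patients continuing treatment receive dupilumab, and SAP 4.3.6 assigns anyone given both products to the dupilumab group, so there is no real placebo comparison. The documents give no reason to link a late visit with weight change.

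**No double-blind weight table is named.** True. Section 9 speaks of all safety results, while 9.3 defines these abnormalities over the TEAE period, which spans both treatment periods. That part of the point is conditional.

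**Conclusion.** The point holds as a small defect of specification. From the documents alone, the target day of the only scheduled post-baseline weight is exactly last dose + 14 days, and the weight abnormality summary admits nothing later. Protocol-compliant late V9 weights are left out. If the boundary is exclusive, on-target weights are left out as well.

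The share cannot be fixed from the documents. It is 43% or 57% under an assumed even spread of visits with the dose on Day 155, and 5% or 95% if 90% of visits fall on Day 169. The more closely visits keep to schedule, the more the unstated boundary rule decides whether almost all or almost no completers count.

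The consequence is limited to one descriptive safety table with an arbitrary denominator and, if the split by period is applied to weight, a double-blind version confined to patients with an early V9. The documents do not support a claim of lost data or of a biased comparison between arms.

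**What to change.** In SAP 9.3:
1. For weight only, include in the abnormality summary the V9 weight of every patient whose last dose was the Week 22 dose; for all others, include weights up to last dose + 14 days.
2. State that day 14 is included.
3. Present weight abnormalities for the overall period only.
4. Correct the sentence that lists weight and height as collected at all visits, to match the schedule.

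The cost is SAP wording and one programming condition, with no new measurement and no change to any efficacy analysis. The downside is that a few weights taken some days past the formal on-treatment period would be counted. A patient who missed the Week 22 dose would still be left out at an on-target V9: the Week 20 dose is on Day 141 and 169 − 141 = 28 days, which is in keeping with an on-treatment table.
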